3.6. Eligibility criteria

Inclusion criteria:

Patient level inclusion criterion

1. 18 years of age or older;

Eye level inclusion criteria - at least one eye must meet all of the following conditions

2. Inactive or minimally active non-infectious anterior, intermediate, posterior or panuveitis, as defined by SUN² criteria as $\leq 0.5+$ anterior chamber cells, $\leq 0.5+$ vitreous haze grade and no active retinal/choroidal lesions for a minimum of 4 weeks;
3. Macular edema (ME) defined as the presence of macular thickness greater than the normal range for the OCT machine being used (see cut points below), regardless of the presence of cysts, following most recent intravitreal corticosteroid injection (≥ 4 weeks following intravitreal triamcinolone injection or ≥ 12 weeks following intravitreal dexamethasone implant injection);

*Greater than 300 μm for Zeiss Cirrus
Greater than 320 μm for Heidelberg Spectralis
Greater than 300 μm for Topcon 3DOCT*

4. Best corrected visual acuity (BCVA) 5/200 or better;
5. Baseline intraocular pressure > 5 mm Hg and ≤ 21 mm Hg (current use of ≤ 3 intraocular pressure-lowering medications and/or prior glaucoma surgery are acceptable (*Note: combination medications, e.g., Combigan, are counted as two IOP-lowering medications*));
6. Media clarity and pupillary dilation sufficient to allow OCT testing and assessment of the fundus.

Exclusion criteria:

Patient level exclusion criteria

1. History of infectious uveitis in either eye;
2. History of infectious scleritis of any type in either eye (*Note: History of noninfectious scleritis that has been active in past 12 months is an eye-level exclusion –see #13 below*);
3. History of keratitis (with the exception of keratitis due to dry eye) in either eye;
4. History of central serous retinopathy in either eye;
5. Active infectious conjunctivitis in either eye;
6. Oral prednisone dose > 10 mg per day (or of an alternative corticosteroid at a dose higher than that equipotent to prednisone 10 mg per day) OR oral prednisone dose ≤ 10 mg per day at baseline that has not been stable for at least 4 weeks (*note: if patient is*

off of oral prednisone at baseline (M01 study visit) dose stability requirement for past 4 weeks does not apply);

7. Systemic immunosuppressive drug therapy that has not been stable for at least 4 weeks (*note: use of systemic methotrexate is acceptable as long as regimen has been stable for at least 4 weeks*);
8. Use of oral acetazolamide or other systemic carbonic anhydrase inhibitor at baseline;
9. Known allergy or hypersensitivity to any component of the study drugs;
10. For women of childbearing potential: pregnancy, breastfeeding, or a positive pregnancy test; unwilling to practice an adequate birth control method (abstinence, combination barrier and spermicide, or hormonal) for duration of trial;

Eye level exclusion criteria - at least one eye that meets all inclusion criteria cannot have any of the following conditions

11. History of infectious endophthalmitis;
12. History of severe glaucoma as defined by optic nerve damage (cup/disc ratio of ≥ 0.9 or any notching of optic nerve to the rim);
13. History of active noninfectious scleritis in past 12 months (*Note: History of noninfectious scleritis is acceptable if the last episode of active scleritis resolved at least 12 months prior to enrollment*);
14. Presence of an epiretinal membrane noted clinically or by OCT that per the judgment of study ophthalmologist may be significant enough to limit improvement of ME (i.e., causing substantial wrinkling of the retinal surface);
15. Torn or ruptured posterior lens capsule
16. Presence of silicone oil;
17. Ozurdex administered in past 12 weeks;
18. Anti-VEGF agent, intravitreal methotrexate, or intravitreal/periocular corticosteroid administered in past 4 weeks;
19. Fluocinolone acetonide implant (Retisert) placed in past 3 years.

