3.1. Type of study

- Randomized, three-arm, parallel design, randomized comparative effectiveness trial
- Randomization stratified by presence or absence of concomitant systemic corticosteroid and/or immunosuppressive therapy for any indication
- Unit of randomization is patient, not eye; if both eyes meet eligibility criteria, both receive same treatment
- Allocation ratio (1:1:1)
- Multicenter
- Fixed sample size, 240 (80 per treatment group)
- Anniversary close-out at the 6-month clinic visit
- Reading center graders and visual acuity examiners will be masked to treatment
- Treating physicians and patients will be unmasked (the intravitreal therapies are different in appearance and have potentially different injection schedules)

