3.8. Data collection schedule

Visit ID	M01	M02	M03	M04	M05	M06	M07
Time	Baseline	4-wk	8-wk	12-wk	16-wk	20-wk	24-wk
Medical/ophthalmic history	X	X	X	X	X	X	X
Treatment history	X	X	X	X	X	X	X
Best-corrected visual acuity	X	X	X	X	X	X	X
Tonometry	X	X	X	X	X	X	X
Ophthalmic exam	X	X	X	X	X	X	X
Gonioscopy	X						
OCT	X	X	X	X	X	X	X
Health utility measures (EuroQOL, VFQ-25)	X	X	X	X	X	X	X
Adverse event monitoring	X	X	X	X	X	X	X
Pregnancy testing	X [†]	X [‡]	X [‡]	X [‡]	X [‡]	X [‡]	X [‡]

[†] Required for all women of childbearing potential at M01

[‡] Required for women of childbearing potential before any additional intravitreal injections of methotrexate or ranibizumab

4. Treatment schedule

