4.2. Study treatment schedule and retreatment criteria

4.2.1. Table: Study treatment schedule by treatment assigned and study visit

Study treatment schedule by treatment assigned and study visit							
Treatment Assignment	Study visits						
	M01 week 0	M02 week 4	M03 week 8	M04 ^{††} week 12	M05 ^{††} week 16	M06 ^{††} week 20	M07 ^{††} week 24
Ozurdex	Required	None	Required if criteria met*	Permitted if criteria met* [†]	Permitted if criteria met* [†]	Permitted if criteria met* [†]	Permitted if criteria met* [†]
Methotrexate	Required	Required if criteria met*	Required if criteria met*	Permitted if criteria met*	Permitted if criteria met*	Permitted if criteria met*	Permitted if criteria met*
Ranibizumab	Required	Required	Required	Permitted if criteria met*	Permitted if criteria met*	Permitted if criteria met*	Permitted if criteria met*

* ME retreatment criteria: Central subfield thickness greater than 1.1X upper limit of normal (330 μ m for Zeiss and Topcon SD OCT and 352 μ m for Heidelberg OCT) and/or cystoid space(s) within 1 mm central subfield; IOP criteria <25 mm Hg (treatment with \leq 3 IOP-lowering agents permitted)

[†] A minimum of 51 days is required between Ozurdex treatments so retreatment will be an option only if the last treatment was administered \geq 51 days previously

^{††} Alternatively, participant may be treated according to the best medical judgment of the study ophthalmologist at the M04 and subsequent visits

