4.2.3. Intravitreal methotrexate, 400 µg in 0.1 mL

- M01: Treatment required
 - Preferably administered on the day of randomization but may be administered up to 10 days after randomization
 - Pre-injection IOP requirements: ≤ 21 mm Hg and ≤ 3 IOP lowering agents*
- M02: Retreatment required if criteria in section 4.2.5 are met
- M03: Retreatment required if criteria in section 4.2.5 are met
- M04 and subsequent visits: Retreatment permitted if the retreatment criteria in section 4.2.5 are met as discussed below and if there has been at least 23 days since the last treatment.

If there has been evidence of a treatment benefit but a participant meets retreatment criteria at the M04 visit, the participant should be encouraged to continue the assigned treatment. However, the participant may be treated according to the best medical judgment of the study ophthalmologist at the M04 and subsequent visits.

- *For women of child-bearing potential, negative pregnancy test required before all injections*

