4.2.4. Intravitreal ranibizumab (Lucentis), 0.5 mg in 0.05 mL

- M01: Treatment required
 - Preferably administered on the day of randomization but may be administered up to 10 days after randomization
 - Pre-injection IOP requirements: ≤ 21 mm Hg and ≤ 3 IOP lowering agents*
- M02: Treatment required
 - Pre-injection IOP requirement: < 25 mm Hg and ≤ 3 IOP lowering agents
- M03: Treatment required
 - Pre-injection IOP requirement: < 25 mm Hg and ≤ 3 IOP lowering agents
- M04 and subsequent visits: Retreatment permitted if criteria in section 4.2.5 and there has been at least 23 days since the last treatment. .

If there has been evidence of a treatment benefit but a participant meets retreatment criteria at the M04 visit, the participant should be encouraged to continue the assigned treatment. However, the participant may be treated according to the best medical judgment of the study ophthalmologist at the M04 and subsequent visits.

- *For women of child-bearing potential, negative pregnancy test required before all injections*

** Note that the IOP requirements for the initial injection are the same as for eye eligibility for the trial. If study treatment is initiated on the same day as eligibility is confirmed and treatment assigned, no additional IOP measurements are needed.*

circumstances require patient to return to clinic for injection at a later date, IOP must be checked and IOP-lowering agents evaluated prior to injection. If the eligibility requirements are not met, the injection should not be given. If the treating ophthalmologist elects to proceed with assigned treatment per best medical judgment, the deviation from the protocol must be reported to CC on an Unanticipated Event (UA) form; the UA form should be submitted as soon as possible.

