4.2.5. Retreatment criteria and pre-injection IOP requirements

- Macular edema warrants retreatment if **one or both** of the following criteria are present:
 - Central subfield thickness greater than 1.1X upper limit of normal (330 μm for Zeiss and Topcon SD OCT and 352 μm for Heidelberg OCT)
 - Cystoid spaces within 1 mm central subfield
- IOP requirements pre-injection: <25 mm Hg and ≤ 3 IOP-lowering agents
- Negative pregnancy test required for women of childbearing potential before every injection of methotrexate or ranibizumab

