8.4.6. Pregnancy

If a female subject becomes pregnant while receiving investigational therapy or within 30 days after the last dose of a study treatment, a report should be completed and expeditiously submitted to the Coordinating Center who will submit report to Genentech, Inc. if study treatment is Lucentis. Follow-up to obtain the outcome of the pregnancy should also occur. Abortion, whether accidental, therapeutic, or spontaneous, should always be classified as serious, and expeditiously reported as an SAE. Similarly, any congenital anomaly/birth defect in a child born to a female subject exposed to a study treatment should be reported as an SAE.

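### Methotrexate or ranibizumab may be injected at the close-out visit (M07), but exclusion 10 ends the contraception commitment with the trial, so an M07 dose has none after it

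*Combined protocol and SAP*

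**What the plan says.** **Late dosing.** In the section 4.2.1 table, the M07 (week 24) entries for methotrexate and ranibizumab both read "Permitted if criteria met". The arm sections agree. For methotrexate, section 4.2.3 has "M04 and subsequent visits: Retreatment permitted if the retreatment criteria in section 4.2.5 are met as discussed below". For ranibizumab, section 4.2.4 has "M04 and subsequent visits: Retreatment permitted if criteria in section 4.2.5 and there has been at least 23 days since the last treatment".

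**End of follow-up.** Section 3.1 specifies "Anniversary close-out at the 6-month clinic visit", and M07 is the last column of the section 3.8 schedule.

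**Contraception.** Exclusion 10 (section 3.6) rules out a woman of childbearing potential who is "unwilling to practice an adequate birth control method (abstinence, combination barrier and spermicide, or hormonal) for duration of trial". No other section supplied adds a requirement or extends this one past the last dose.

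**Pregnancy testing.** A test is required for all women of childbearing potential at M01. After that, the section 3.8 footnote, which is also attached to M07, says "Required for women of childbearing potential before any additional intravitreal injections of methotrexate or ranibizumab". Section 4.2.5 repeats it: "Negative pregnancy test required for women of childbearing potential before every injection of methotrexate or ranibizumab".

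**Pregnancy reporting.** Section 8.4.6 asks for a report if a participant "becomes pregnant while receiving investigational therapy or within 30 days after the last dose of a study treatment".

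**The concern.** The protocol takes pregnancy seriously for these two drugs. It excludes pregnant and breastfeeding women, requires a negative test before each injection, and in section 5.4.1 describes methotrexate as cytotoxic. A test on the day of injection excludes a pregnancy that already exists. It does nothing about conception in the days that follow; only the contraception commitment does that. Because the commitment is tied to the trial and not to the last dose, it runs out just when the last permitted dose is given. A woman could be injected at M07 and, on the protocol text, stop contraception the same day. What is at stake is the safety of a participant and a possible pregnancy. No estimate or test in the trial is involved.

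**Working it through.** There is no figure in the plan to reproduce. The check is to set the dosing, follow-up and contraception rules side by side and count days.

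**Inputs**
- Visit days (section 3.8, nominal): M05 at week 16, M06 at week 20, M07 at week 24.
- End of the contraception commitment: the end of the trial (exclusion 10), taken as the participant's own close-out at M07 (section 3.1), day 24 × 7 = 168.
- Window after a dose: 30 days (section 8.4.6). It serves as the yardstick because it is the only post-dose pregnancy period that the protocol gives.

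**Formulas**
- Window end = dose day + 30.
- Days covered = min(30, 168 − dose day).
- Days not covered = 30 − days covered.

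| Last dose at | Dose day | Window ends | Days covered | Days not covered |
|---|---|---|---|---|
| M05 | 16 × 7 = 112 | 142 | min(30, 56) = 30 | 0 |
| M06 | 20 × 7 = 140 | 170 | min(30, 28) = 28 | 2 |
| M07 | 24 × 7 = 168 | 198 | min(30, 0) = 0 | 30 |

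The 2 days for M06 are within ordinary variation in visit timing and carry no weight. The M07 row matters, because it follows from dosing on the close-out day itself.

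**Sensitivity to the meaning of the trial's duration.** The term is not defined. If it meant the whole trial rather than the participant's own follow-up, women who closed out early would be covered. If the whole trial ends with the last close-out visit, the last participant to close out would still have 0 of 30 days after an M07 dose.

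**With the commitment extended to 30 days after the last injection**, cover after an M07 dose runs to day 168 + 30 = 198, and the days not covered fall from 30 to 0.

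**The case against.** **The consent form may already cover this.** Consent pages were not part of the material, and the Manual of Procedures was not available, so a longer commitment in either cannot be ruled out. That stands as a limit on the finding. But exclusion 10 is present and states its own end point, so the rule itself can be judged, and it should agree with whatever the consent form says.

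**Thirty days is a reporting window.** This stands. A reader might infer that the protocol recognises 30 days of fetal risk after a dose. It does not: section 8.4.6 only fixes when a pregnancy must be reported, and a reporting window may properly outlast the contraception period. The only post-dose duration given for methotrexate is a therapeutic concentration in the eye for 48 to 72 hours (section 1.6), which settles neither risk nor safety. What remains is that a commitment of zero days after a dose is not supported either.

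**Pregnancies after M07 would still be captured.** A reader might infer that they fall outside reporting. The documents say otherwise. Section 8.4.6 requires a report up to 30 days after the dose, with follow-up of the outcome. Section 8.4.11 sets no end date for pregnancy reports after ranibizumab. Section 8.4.8 keeps attributed serious events, and congenital anomalies in a child conceived later, reportable after the study. No test or visit is scheduled after M07, but that is true of a dose at any final visit.

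**M07 dosing is optional.** It needs the retreatment and pressure criteria and at least 23 days since the last injection. From M04 the ophthalmologist may use other treatment instead, and eyes that have not improved at M06 pass to medical judgment (section 4.3). This makes the affected group small. It does not remove M07 dosing, which the treatment table permits and the visit schedule provides a pregnancy test for.

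**Adverse-event reporting.** A reader might also infer that such reporting stops at M07. Section 8.3.1 ends it 30 days after the last dose or when the study is discontinued or terminated, if that comes first. If close-out counts as termination, non-serious events and unattributed serious events after an M07 dose would not be reported. If the phrase means early withdrawal only, which the distinction in section 8.4.8 between completing and discontinuing could suggest, there is no gap. The text does not decide, so this is a possible ambiguity and not an established defect.

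**Conclusion.** The point holds as a participant-safety wording gap. On the protocol text, a woman given methotrexate or ranibizumab at M07 has no contraception commitment after that dose: 0 of the 30 days for which the protocol wants pregnancies reported, against 28 after M06 and 30 after M05. This assumes nominal visit days and that the commitment ends at the participant's own close-out.

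The documents do not give the number of women of childbearing potential injected at M07. It is probably small, since the group is limited to two arms and to optional injections at one visit. Nor do the documents say what contraception period either drug needs. Efficacy results are untouched, and the safety outcomes in section 3.5 are defined over 24 weeks of follow-up, so no planned analysis changes. It is a cheap improvement worth making, and not a flaw in the design.

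**What to change.** In exclusion 10, require contraception for the duration of the trial and for a stated period after the last methotrexate or ranibizumab injection. Set that period to at least the 30 days of section 8.4.6, and have the sponsor confirm the length against product labelling, since the protocol itself supports no particular figure. Align the consent form if it does not already say this.

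The cost is one phrase in the protocol, perhaps one line in the consent form, and a slightly longer commitment for the few women injected late. No extra visit or contact is needed.

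An edit to section 8.3.1 is optional. If it is made, adverse-event reporting should end at the later of close-out and 30 days after the last study injection, so that the change does not shorten reporting for participants whose last injection was early.

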3.7. Randomization

After the patient has given written informed consent, eligibility has been confirmed and baseline data have been keyed and passed an electronic eligibility review, the patient will be randomly assigned to one of the three treatment groups, via a web-based system, returning the treatment assignment result in real time. Beginning at this point, the patient's data will be included for primary analyses, regardless of subsequent actual treatment and/or extent of adherence to therapy. Randomization will be accomplished using an auditable, documented scheme

generating a reproducible order of assignment. Randomization schedules will be developed by the Coordinating Center (CC), using permuted blocks of varying lengths, designed to yield expected assignment ratio of 1:1:1. Randomization will be stratified by presence or absence of concomitant systemic corticosteroid and/or immunosuppressive therapy for any indication

3.8. Data collection schedule

Visit ID	M01	M02	M03	M04	M05	M06	M07
Time	Baseline	4-wk	8-wk	12-wk	16-wk	20-wk	24-wk
Medical/ophthalmic history	X	X	X	X	X	X	X
Treatment history	X	X	X	X	X	X	X
Best-corrected visual acuity	X	X	X	X	X	X	X
Tonometry	X	X	X	X	X	X	X
Ophthalmic exam	X	X	X	X	X	X	X
Gonioscopy	X						
OCT	X	X	X	X	X	X	X
Health utility measures (EuroQOL, VFQ-25)	X	X	X	X	X	X	X
Adverse event monitoring	X	X	X	X	X	X	X
Pregnancy testing	X [†]	X [‡]	X [‡]	X [‡]	X [‡]	X [‡]	X [‡]

[†] Required for all women of childbearing potential at M01

[‡] Required for women of childbearing potential before any additional intravitreal injections of methotrexate or ranibizumab

4. Treatment schedule

4.1. Overview

- Study participants are randomized to receive one of three treatments in eye(s) meeting eye-level eligibility criteria at baseline (M01)

Note: If only one eye is eligible at baseline then that eye will be the only study eye throughout the trial. If the second eye “meets eligibility criteria” later at a later time point, the second eye does not become a study eye. Rather the second eye is treated per best medical judgment of the study/ treating ophthalmologist.

- The timing of initial injections of assigned treatment, required 2nd and 3rd injections in ranibizumab group, and retreatment for all groups are specified in section 4.2 below
- All injections of study treatments must be administered per protocol instructions and follow relevant IOP pre-injection criteria
 - Initial injection of study treatment: IOP \leq 21 mm Hg and \leq 3 IOP-lowering agents
 - Retreatment: IOP $<$ 25 mm Hg and \leq 3 IOP-lowering agents
- Pregnancy testing required for women of childbearing potential before additional intravitreal injections of methotrexate or ranibizumab
- Treatment according to the best medical judgment of study ophthalmologist is permitted as deemed necessary. Repeat injections given before the protocol specified time points (section 4.2.6) or other deviations from the treatment protocol should be reported expeditiously to CC on Unanticipated Event (UA) form.

4.2. Study treatment schedule and retreatment criteria

4.2.1. Table: Study treatment schedule by treatment assigned and study visit

Study treatment schedule by treatment assigned and study visit							
Treatment Assignment	Study visits						
	M01 week 0	M02 week 4	M03 week 8	M04 ^{††} week 12	M05 ^{††} week 16	M06 ^{††} week 20	M07 ^{††} week 24
Ozurdex	Required	None	Required if criteria met*	Permitted if criteria met* [†]	Permitted if criteria met* [†]	Permitted if criteria met* [†]	Permitted if criteria met* [†]
Methotrexate	Required	Required if criteria met*	Required if criteria met*	Permitted if criteria met*	Permitted if criteria met*	Permitted if criteria met*	Permitted if criteria met*
Ranibizumab	Required	Required	Required	Permitted if criteria met*	Permitted if criteria met*	Permitted if criteria met*	Permitted if criteria met*

* ME retreatment criteria: Central subfield thickness greater than 1.1X upper limit of normal (330 μ m for Zeiss and Topcon SD OCT and 352 μ m for Heidelberg OCT) and/or cystoid space(s) within 1 mm central subfield; IOP criteria <25 mm Hg (treatment with \leq 3 IOP-lowering agents permitted)

[†] A minimum of 51 days is required between Ozurdex treatments so retreatment will be an option only if the last treatment was administered \geq 51 days previously

^{††} Alternatively, participant may be treated according to the best medical judgment of the study ophthalmologist at the M04 and subsequent visits

